## 2.2 Intermediate statistical analysis

The study does not plan to conduct an intermediate statistical analysis.

# 2.3 Planned number of participants in a clinical trial with justification of sample size

The calculation of the sample size is based on the study results of the medical device NOLTREX TM for OA (osteoarthritis) of the knee joint (N. V. Zagorodny et al. The use of new biopolymer material Noltrex in the complex treatment of patients with gonarthrosis. 2012, t. 17, No. 6, p. 49-52)[3]. Application in this study during the first 10 days of NSAID Movalis does not affect the assessment of results after 13 and 25 weeks.

As the primary endpoint in the study the change in total score on the WOMAC scale in the affected joint (WOMAC total) was chosen, at Visit 7 (week 25) compared to the basal value at Visit 1 (week 1). The choice of "Week 25" assessment point is related to the fact that in the above study the effect of medical device NOLTREX TM was maximal after 6 months from the injection, and then the effect of the treatment was decreasing. An additional endpoint - a change in the total score on the WOMAC

scale (WOMAC total) at Visit 6 (week 13) compared to the basal value at Visit 1 (week 1) will be used to assess the onset of the effect of medical device after 3 months from the injection.

For the calculations the following assumptions were used:

- 1) Two groups (fixed factor A) medical device NOLTREXTM and placebo
- 2) Baseline of WOMAC level and the total dose of NSAIDs received in the duration of study as covariates
- 3) Effect size 0.25: calculated on the basis of data from the above publication, in which the magnitude of differences between groups, taking into account the variability, was up to 100 points, and the variability (standard deviation) up to 400 points
- 4) Level of significance = 5% (type I error  $\alpha$  = 0.05)
- 5) Power 80% (type II error  $\beta$  = 0.20)
- 6) Statistical model covariance analysis (adjusted for the initial value) with fixed factors of the group
- 7) Drop-outs during the study will not exceed 10%.
- 8) Drop-out during inclusion period (screening) will not exceed 15%.

Calculations of the sample size (the number of completed cases) were performed using the G\*Power 3.1.9.2 software package with the above assumptions:

F tests - ANCOVA: Fixed effects, main effects and interactions

A priori: Compute required sample size Analysis: Input: Effect size f = 0.25= 0.05α err prob Power (1–β err prob) = 0.80= 1 Numerator df Number of groups = 2 Number of covariates = 2 = 8.0000000 Output: Noncentrality parameter  $\lambda$ Critical F = 3.9175498Denominator df = 124 = 130 Total sample size Actual power = 0.8013621

In this case, taking into account rounding, the study should complete 130 patients (65 in each group), for which it is necessary to randomize 144 patients (72 in each group).

Accordingly, to achieve the required number of randomized patients, it is necessary to screen up to 170 patients.

## 2.4 Applicable level of significance

For all parameters of efficacy, safety and tolerability the bilateral statistical criteria will be used at a 95% significance level (the threshold value p for confirming statistical significance is less than 0.05).

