## 2 Description of statistical methods

### 2.1 Description of statistical methods to be used

Statistical analysis will be carried out using specialized software, the selection of which will be carried out during the preparation of the statistical analysis plan.

Continuous (quantitative) data will be presented using the number of observations, arithmetic mean, 95% confidence interval (CI) for mean, standard (mean-square) deviation, median, interquartile range (25th and 75th centile), minimum and maximum.

Qualitative data (ordinal, nominal) will be presented using absolute frequencies (number of observations), relative frequencies (percent) and 95% CI.

Unless otherwise specified in the statistical analysis plan, statistical tests will be two-sided with a 5% confidence level.

The medical history and AEs will be encoded using the MedDRA classifier in the current version. Concomitant and prior therapy will be encoded using the ATX classifier.

This section briefly describes the planned analysis. The full analysis will be described in the statistical analysis plan.

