#### 2.1.3 Analysis of secondary efficacy parameters

An analysis of the following secondary efficacy parameters is planned:

- Changing the overall score on the WOMAC scale (WOMAC-T) on Visit 4 (week 13) compared to the basal value on Visit 1 (week 1);
- The change in score on the subscale of pain (WOMAC-A) on Visit 3 (week 6), Visit 4 (week 13) and Visit 5 (week 25) and compared with the basal value on Visit 1 (week 1);
- The change in the score for the stiffness (WOMAC-B) and functionality (WOMAC-C) on Visit 3 (week 6), Visit 4 (week 13) and Visit 5 (week 25) compared to the basal value on Visit 1 (week 1);
- Evaluation of the treatment efficacy by the patient, the value OEP (on a scale of 1 a clear deterioration to 6 a significant improvement) at visits 3, 4 and 5 (OEP-w6, OEP-w13, OEP-w25);
- Evaluation of the effectiveness of treatment by the investigator, the value OEI (on a scale of 1 a clear deterioration to 6 a significant improvement) on visits 3, 4 and 5 (indicators OEI-w6, OEI-w13, OEI-w25);
- Assessment as per patient diary of the total number of paracetamol tablets taken (one tablet = 500 mg) starting on day 1, on visits 3, 4 and 5 (PARACETAMOL-w6, PARACETAMOL-w13 and PARACETAMOL-w25, respectively);
- Assessment per patient diary of the total number of NSAID tablets, starting on day 1, at visits 3, 4, 5 (values NSAID-w6, NSAID-w13 and NSAID-w25, respectively)
- Drop-out rate due to safety (exclusion criteria 2, 3, 6, 7);
- Drop-out rate due to low patient adherence to treatment (criteria 4 and 5).

For secondary efficacy parameters, the following statistical analysis methods are planned:

- For quantitative indicators, an analysis similar to the analysis of the primary endpoint (covariance analysis) followed by the identification of groups with significant differences using Tukey's HSD.
- For frequency indicators (segments) comparison of groups using the  $\chi^2$  criterion ("chi-square").

Analysis of secondary efficacy parameters will be conducted on the ITT population (main analysis) and on the PP population (additional analysis).

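### SAP 2.4 sets one p<0.05 threshold for every parameter, and the 24 secondary comparisons in SAP 2.1.3 have no order, no link to the primary result and no correction across endpoints or visits

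*SAP*

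**What the plan says.** SAP 2.1 sets the default: "Unless otherwise specified in the statistical analysis plan, statistical tests will be two-sided with a 5% confidence level". SAP 2.4 repeats it without separating primary from secondary: "For all parameters of efficacy, safety and tolerability the bilateral statistical criteria will be used at a 95% significance level", and then defines the cut-off as "the threshold value p for confirming statistical significance is less than 0.05".

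SAP 2.1.2 names one primary hypothesis, on the change in WOMAC-T from baseline to Week 25, with ITT as the main analysis and PP as additional. SAP 2.1.3 lists the secondary efficacy parameters: the change in WOMAC-T at Week 13; the pain, stiffness and function subscales at Weeks 6, 13 and 25; patient and investigator ratings at three visits; cumulative paracetamol and NSAID tablets at three visits; and two drop-out rates. Quantitative parameters are analysed by ANCOVA followed by Tukey's HSD, and frequencies by chi-square. Each parameter is analysed on ITT and again on PP.

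Neither document states a testing order, a gatekeeping rule, a split of alpha, or an adjustment across endpoints or visits. Neither describes the secondary or safety tests as supportive or exploratory.

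**The concern.** The 5% level belongs to one hypothesis, but the same wording governs every other comparison. A report that follows SAP 2.4 literally could present a significant stiffness result at Week 6, or a significant patient rating at Week 13, in the same terms as the primary result, even if Week 25 WOMAC-T shows nothing. No stated rule tells the reader that the two kinds of result carry different error rates. What is at stake is how secondary findings are read, not the validity of the primary test.

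**Working it through.** **The plan's own figure.** The documents state no error rate for the secondary family, so there is none to reproduce. What can be reproduced is the scope of the stated alpha. The sample-size calculation (SAP 2.3) is for one F test with 1 numerator df, f = 0.25, alpha = 0.05 and two covariates. With λ = f²·N = 0.0625 × 128 = 8.0 and denominator df = 128 − 4 = 124, the critical F is 3.9175 and the power 0.8014, as printed. (The printed λ and df belong to N = 128 rather than the stated 130; this does not bear on the present point.) The 5% is therefore planned for one comparison.

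**Count of secondary comparisons (SAP 2.1.3).**

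| Parameter | Comparisons |
|---|---|
| WOMAC-T, Week 13 | 1 |
| WOMAC-A, Weeks 6, 13, 25 | 3 |
| WOMAC-B and WOMAC-C, Weeks 6, 13, 25 | 6 |
| Patient rating (OEP), three visits | 3 |
| Investigator rating (OEI), three visits | 3 |
| Paracetamol tablets, three visits | 3 |
| NSAID tablets, three visits | 3 |
| Drop-out for safety; drop-out for low adherence | 2 |
| **Total** | **24** |

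This counts one device-placebo test per endpoint and visit, on ITT only.

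**Independence.** With no true effect on any of the 24:

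- Expected number significant: 24 × 0.05 = 1.2.
- At least one in either direction: 1 − 0.95^24 = 1 − 0.292 = 0.708.
- At least one favouring the device (2.5% per test): 1 − 0.975^24 = 1 − 0.545 = 0.455.

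**Correlation.** The documents give no correlations, so these are assumed. For jointly normal statistics with common correlation ρ, the chance of at least one significant result was obtained by numerical integration over the shared component, with all statistics oriented so that benefit is positive.

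| Assumed ρ | Either direction | Favouring the device |
|---|---|---|
| 0 | 71% | 46% |
| 0.3 | 59% | 31% |
| 0.5 | 46% | 23% |
| 0.7 | 31% | 16% |

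For two-sided tests on jointly normal statistics, independence is the worst case (Šidák's inequality), so 71% is an upper bound. The 46% is an upper bound provided the benefit-oriented statistics are not negatively correlated. A block structure (assumed correlation 0.6 to 0.8 across visits within an endpoint, 0.3 to 0.6 between endpoints, and 0.1 for the two drop-out rates) gives about 41% to 55% in either direction. Leaving out the two drop-out rates changes the bound little: 1 − 0.95^22 = 68%.

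**Does Tukey's HSD help?** With two arms its critical value, on the t scale at 124 df, is 1.979, the same as the t-test's, so it corrects nothing. Applied to four cells (two arms by two radiological grades) it rises to 2.604, a per-comparison level of about 0.010. That limits error among the contrasts of one endpoint at one visit, not across the 24. The figures above refer to the 5% test of the group factor.

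**The case against.** Several objections have force.

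- *The primary is protected.* There is one primary endpoint, one stated null hypothesis and one sample-size calculation, with ITT ahead of PP. This stands: the listed secondaries leave the 5% error of the Week 25 test untouched.
- *The wording is about significance, not effect.* SAP 2.4 defines when a p-value is called significant. It does not say that a significant secondary establishes a benefit or rescues a failed primary. A reader might infer that one secondary at p = 0.04 counts as a confirmed effect; no sentence says so. What remains is that no sentence rules it out.
- *The 71% is not a realistic estimate.* This also stands. The subscales belong to the same questionnaire as WOMAC-T, the same patients are measured repeatedly, and the tablet totals run from day 1, so later counts contain earlier ones. Independence cannot hold.
- *Half of the false results would favour placebo.* Correct. A reader might infer from 71% that an ineffective device would probably still show a significant benefit. The matching figure is at most 46%, and lower with correlation, so that inference fails.
- *Details are deferred.* SAP 2.1 calls its account brief and points to a fuller plan, which might hold a multiplicity rule. The SAP supplied contains none, and SAP 2.4 states its threshold without a reservation, so the deferral does not close the gap.
- *PP and safety comparisons should not swell the tally.* Fair: PP largely reuses the same patients, and a chance excess of adverse events on the device is not a false efficacy claim. Both are left out of the figures.

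**Conclusion.** The point holds as a gap in how secondary results may be interpreted. One threshold covers everything, and 24 secondary comparisons carry no control across endpoints or visits. With no true effect on any of them, a significant secondary favouring the device would arise with probability between 16% (ρ = 0.7) and 46% (independence), about 6 to 18 times the 2.5% for a single test. In either direction the range is 31% to 71%. These figures rest on the global null, one 5% test per comparison, joint normality and the assumed correlations; the upper ends are bounds rather than expectations.

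The finding does not extend to the primary test, and it does not show that the sponsor intends to claim success on secondaries alone. It is a change that should be made, not a flaw that invalidates the trial.

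**What to change.** In SAP 2.4, replace the single rule with two statements. First, confirmatory conclusions are limited to the primary test (WOMAC-T, Week 25, ITT) at two-sided 5% and, only if it succeeds, to a short prespecified sequence, each step tested at two-sided 5% only while every earlier step has succeeded. One possible sequence is WOMAC-A at Week 25, then WOMAC-C at Week 25, then WOMAC-T at Week 13; the order is for the sponsor to choose, before unblinding. Second, all other secondary comparisons, all PP results and all safety comparisons are reported as estimates with 95% CIs and nominal p-values that support no confirmatory claim. SAP 2.1.3 should refer to this rule and say that Tukey's HSD does not control error across endpoints or visits.

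A simpler alternative is to declare all secondaries supportive, which closes the gap but gives up any confirmatory secondary claim.

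The change is a few sentences. It needs no extra patients, visits or data, and the power of the primary test is unchanged. The cost is that secondaries outside the sequence, or after a failed step, cannot be called confirmed however small their p-values.

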### 2.5 Study termination criteria

The study can be stopped for the following reasons:

- 1. At the initiative of the sponsor:
- a. obtaining new toxicological or pharmacological data, or data on SAE, which force to revise the previously conducted assessment of the benefits/risks of participation in the study;
- b. the frequency of AE and/or their severity does not allow to continue the study;
- c. other reasons, including administrative.
- 2. At the initiative of the investigator: the frequency of AE and/or their severity unacceptably increases the risk for patients participating in the study
- 3. by decision of regulatory authorities.

If the study is preliminary ended, the Sponsor is obliged to notify the personnel of the research centers, as well as the regulatory bodies, indicating the reason for the early termination of the study.

The rules for terminating the study for each study participant are listed in section 6.3.

## 2.6 Procedures to count the missing, non-analyzable and questionable data

During the monitoring visits to the clinical center, the monitoring specialists authorized by the sponsor will conduct an analysis of patient's eCRF to identify any lack of necessary data. In the absence of data in the eCRF and the availability of relevant information in the primary documentation, the questions to the investigators and instructions for eliminating the inconsistencies will be formulated.

The statistician, authorized by the sponsor, and the principal investigator, when checking the database of research results, will analyze for the presence of dubious, missing and non-analyzable data, and will also formulate questions to investigators.

Investigators, if possible, will eliminate the identified errors in eCRF and inform the main investigator and authorized representatives of the sponsor about this. If the detected errors in the data cannot be eliminated after the completion of patient participation in the study, the statistical analysis of the data will be used to analyze the sensitivity of the resulting parameters to the doubtful data found. Information about the missing, doubtful and non-analyzable data will be presented in the final clinical trial report.

The missing data for the primary efficacy parameter will be replenished by the last observation carried forward (LOCF) method (transfer of data from the last available observation point to the point for the main analysis).

For the remaining parameters of efficacy, safety and tolerability, data replenishment is not provided.

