Every week between Visits 2 and 3 (weeks 3, 4 and 5), the study personnel contacts a patient by the phone to learn about complaints, AE and need of paracetamol and NSAID intake for the previous 2 weeks. If any AE or need of paracetamol and NSAID intake for over 4 days a week during each of the successive 2 weeks is found, the patient is invited to the clinic for the Unscheduled visit or Premature study discontinuation visit (depending on the visit reason).

Follow-up period (Weeks 3–25)

Visit 3 (Week 6, Day 36 ± 2)

The following procedures will be done:

- Collection of complaints and medical history;
- Recording of concomitant therapy;
- Measurement of body weight;
- Assessment of vital signs (BP, HR, RR, body temperature);
- Physical joint examination;
- Assessment of the patient diary;
- Dispensing of the new patient diary to the patient;
- Completion of algofunctional questionnaire WOMAC with the assessment of pain (WOMAC-A-w₆), stiffness (WOMAC-B-w₆), functionality (WOMAC-C-w₆) subscales and total score (WOMAC-T-w₆) ("Week 6" values);
- Patient's assessment of the treatment efficacy, OEP-w₆ value (per the scale from 1 – evident aggravation to 6 – significant improvement);
- Investigator's assessment of the treatment efficacy, OEI-w₆ value (per the scale from 1 – evident aggravation to 6 – significant improvement);
- Assessment of the total number of paracetamol tablets taken per the patient diary (one tablet = 500 mg), value PARACETAMOLw6;
- Assessment of the total number of NSAID tablets taken, value NSAID-w₆
- Complete blood count;

- Blood biochemistry: glucose, ALT, AST, ALP, GGTP, total bilirubin, creatinine, uric acid;
- Coagulogram (APTT, PT, prothrombin index, fibrinogen);
- Urine analysis;
- Express urine pregnancy test for women with the preserved reproductive potential;
- AE assessment;
- Assessment of the subject exclusion criteria.

On Weeks 8, 10 and 12, the study personnel contacts the patient by the phone to learn about complaints, adverse events (AE) and need of paracetamol and NSAID intake for the previous 2 weeks. If any AE or need of paracetamol intake for over 4 days a week during each of the successive 2 weeks is revealed, the patient is invited to the clinic for the unscheduled visit or premature study discontinuation visit (depending on the visit reason).

Visit 4 (Week 13, Day 84 ± 2)

The following procedures will be done:

- Collection of complaints and medical history;
- Recording of concomitant therapy;

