## 2.8 Selection of study participants for analysis

#### 2.8.1 Population selected on the basis of prescribed treatment (ITT)

For the ITT data set, also known as the full analysis set (FAS), all randomized participants are included who were treated with the medical device under the study, regardless of the extent to which the protocol was followed during the study. This data set is essential for analyzing primary and secondary efficacy parameters.

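### SAP 2.6 fills missing week-25 WOMAC-T by LOCF alone, and the supplied text plans no analysis that varies that assumption: a modest risk, cheaply removed

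*SAP*

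**What the plan says.** SAP 2.6 gives one rule for the primary endpoint: "The missing data for the primary efficacy parameter will be replenished by the last observation carried forward (LOCF) method", explained as "transfer of data from the last available observation point to the point for the main analysis". For everything else, "For the remaining parameters of efficacy, safety and tolerability, data replenishment is not provided". SAP 2.1.2 analyses the change in WOMAC-T to week 25 by ANCOVA, on the ITT set (main) and the PP set (additional). SAP 2.8.1 defines ITT as the set in which "all randomized participants are included who were treated with the medical device under the study", whatever their adherence.

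The only sensitivity wording is also in SAP 2.6. Where detected errors cannot be corrected, the analysis will "analyze the sensitivity of the resulting parameters to the doubtful data found". SAP 2.1 adds: "This section briefly describes the planned analysis. The full analysis will be described in the statistical analysis plan".

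On exit, Subject exclusion criterion 2 in the Protocol removes patients with sustained paracetamol or NSAID need for knee osteoarthritis. Contact starts early: "Every week between Visits 2 and 3 (weeks 3, 4 and 5), the study personnel contacts a patient by the phone", and a call can lead to a discontinuation visit. The first scheduled post-baseline WOMAC is at week 6. The discontinuation visit repeats the Visit 5 procedures, which include WOMAC.

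**The concern.** LOCF treats the score at exit as the score the patient would have had at week 25. Two features of this trial make that doubtful. Some exits are tied to symptoms by rule. The sponsor also expects a slow onset (Protocol, Study methodology) and an effect that was greatest at 6 months in the cited study (SAP 2.3). A score from week 4 or week 10 is then not a week-25 score on the sponsor's own reasoning, and the week-25 difference depends partly on when and why patients left.

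Nothing planned would measure this for WOMAC-T. The PP analysis changes which patients are analysed (SAP 2.8.2), not how gaps are filled. SAP 2.1.3 compares the "Drop-out rate due to safety (exclusion criteria 2, 3, 6, 7", and the week-25 subscales are analysed without imputation. Both are only indirect signs.

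SAP 2.6 also does not state outright that the discontinuation-visit score is the one carried, or what applies to a treated patient with no post-baseline WOMAC.

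**Working it through.** **Planned loss.** The printed G*Power output is reproduced at N = 128: lambda = 0.25² × 128 = 8.0, denominator df = 128 - 2 - 2 = 124, critical F 3.9175, power 0.8014. The plan rounds up to 130. Randomizing 144 allows 14/144 = 9.7% loss, consistent with the stated maximum of 10%.

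**Inputs from the documents.** SD 400 (SAP 2.3). The f = 0.25 entered equals a two-group standardized difference of 0.5, so 0.5 × 400 = 200 points. Because SAP 2.3 also mentions 100 points, 100 was run as well. Exit is about 10%, with 72 per arm. Standard error of the difference: 400 × √(2/72) = 66.7.

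**Assumptions, not in the documents.** Exchangeable visit correlation 0.6; placebo change -100; exit at week 4, 10 or 19 with probability 0.15 to 0.19 if the score then was worse than +150. Every exit is therefore outcome-driven. The link from analgesic days to WOMAC is also assumed.

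**Simulation.** One million patients per arm. The table gives the error in the week-25 difference against the full-data difference; negative means the device's benefit is understated.

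| Method | No effect by week 6 | Half by week 6 | Constant |
|---|---|---|---|
| LOCF, exit-visit score carried | -12.2 | -2.0 | +9.1 |
| LOCF, last scheduled score, or baseline | -17.1 | -11.2 | -7.6 |
| Available cases | -4.4 | -8.8 | -16.3 |
| Mixed model, scheduled scores only | -1.6 | -3.9 | -9.3 |
| Imputation using the exit score | -0.4 | -0.7 | -0.9 |

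Repeat runs put the first row at about -13 / -2 / +9. The largest error is 17.1/66.7 = 0.26 SE; with the exit score carried it is about 13/66.7 = 0.20 SE. With a true difference of 100, LOCF with the exit score errs by -6% to +4%.

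**Hand check on the slow course.** Suppose 10% leave for reasons unrelated to outcome, equally at weeks 4, 10 and 19, and the effect rises linearly from 0 at week 6 to 200 at week 25. The share of the effect not yet reached is 1, 15/19 and 6/19, mean 0.70. The error is 0.10 × 200 × 0.70 = 14 points against the device. The slow-onset error thus comes mainly from timing; the positive error needs outcome-driven or unequal exit.

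**No true effect.** With equal exit the LOCF error is 0. With 13.3% versus 7.0% exit it is +13 points, or 13/66.7 = 0.195 SE. Two-sided type I error is then Φ(-1.96 + 0.195) + Φ(-1.96 - 0.195) = 0.039 + 0.016, about 5.4%. The mixed model on scheduled scores errs by -12 in the same case and the imputation by -1.

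**Would the exit-rate comparison show it?** Simulated exit rates (placebo/active) were 10.9/9.1, 12.0/8.1 and 13.3/6.7%. At 72 per arm, a chi-square test reaches p < 0.05 in only about 6% to 26% of trials.

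**A usable imputation.** Completers have no discontinuation-visit score, so it cannot enter as an ordinary auxiliary variable. Assigning week-4 exits to week 6, and week-10 and week-19 exits to week 13, gave errors of about -1 to 0. The error stayed within about 1 point when roughly half of the exits were unrelated to outcome.

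**The case against.** **The fuller plan may cover this.** That stands as a condition on the whole point.

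**There is a sensitivity sentence.** It applies to errors that cannot be corrected and to doubtful data. The next sentence of SAP 2.6 lists missing data as a separate category. It does not vary LOCF.

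**The scenarios are severe.** The Protocol lists twelve exit reasons, many unrelated to symptoms, and the 10% covers them all. This stands for the positive error, which is near the upper range at that rate. It does not shrink the slow-onset error, as the hand check shows.

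**LOCF mostly works against the device.** Under the courses the documents describe, this stands. The positive error needs a constant effect, contrary to the stated slow onset, or unequal exit between arms.

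**The carry rule is clear enough.** Taken literally, the last available observation is the discontinuation-visit score, or baseline if nothing else exists. That is the natural reading, so the 5-to-17-point gap between the two LOCF rows should not be counted as a likely error. One explicit sentence would still settle it.

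**A mixed model is not clearly better.** This stands. On scheduled scores alone it errs by as much as LOCF in the constant course (-9 against +9) and in the null case (-12 against +13). The imputation's advantage is partly built in, since simulated exit depends on the very score it uses; a few percent could remain if patients leave because of worsening that no score captures.

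**Conclusion.** The point holds for the supplied text: LOCF is the sole method for missing week-25 WOMAC-T, and no planned analysis tests it. The plausible error is about -13 to +9 points on a true difference of 200, and about -13 to -2 under slow onset. No carry rule exceeded about 0.26 SE. These figures rest on the assumed correlation, exit mechanism and time courses. A shift of this size would matter mainly if the result lies close to the significance limit.

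A reader might infer that LOCF favours the device, that it materially inflates the type I error, or that the primary ANCOVA must give way to a mixed model. The documents support none of these. Their own time course points the other way, the unequal-exit null case gives only about 5.4%, and a mixed model on scheduled scores is no better than LOCF in some runs. Nor can it be said that the trial has no such analysis at all, because the fuller plan has not been seen. This is a worthwhile improvement, not a fatal fault.

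**What to change.** In SAP 2.6, before database lock:

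1. Keep the SAP 2.1.2 ANCOVA at week 25, but replace LOCF with multiple imputation by arm for all treated patients, using baseline, week-6 and week-13 WOMAC-T.
2. Assign the discontinuation-visit score by a stated rule to a scheduled visit before week 25: for example, exits before week 6 to week 6 and later exits to week 13. Say what happens when a scheduled week-13 score already exists. Never enter the exit score as an observed week-25 value unless it falls in the Visit 5 window (Day 169 ± 2).
3. Keep LOCF as a sensitivity analysis, stating that the discontinuation-visit score is carried, and baseline if no post-baseline score exists.
4. Add one delta-adjusted or reference-based version of the imputation. In the runs, a delta of 100 on active-arm exits lowered the difference by 7 to 9 points, and a reference-based version by 4 to 16.
5. If the fuller plan already contains such an analysis, cite it in 2.6 instead.

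Cost: an imputation model to pre-specify and modest programming. WOMAC is already collected at every visit needed, and the sample size does not change. Precision is almost unchanged: at 72 per arm the simulated spread was 67 to 70 for LOCF and 68 to 71 for imputation using the exit score.
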